2. OVERALL SYNOPSIS OF THE CLINICAL INVESTIGATION

Clinical investigation title:	Validation Study of Mean Arterial Pressure (MAP) Parameter of Masimo INVSENSOR00073
Study objective(s):	The objective of this study is to validate the Mean Arterial Pressure (MAP) parameter of Masimo INVSENSOR00073 against the gold standard blood pressure measurements from the arterial line.
Study device under test:	Masimo INVSENSOR00073
Number of participants:	Approximately 20.
Inclusion criteria:	
Influenced by study design:
 
• Subject is 18 to 40 years of age.• Subject weighs a minimum of 110 lbs.• Baseline heart rate \geq 45 bpm and \leq 90 bpm.• Baseline blood pressure: Systolic blood pressure \leq 135 mmHg and \geq 100 mmHg. Diastolic blood pressure \leq 95 mmHg and \geq 55 mmHg. Valid systolic blood pressure (SBP) auscultatory measurements for lateral difference is \leq 15 mmHg. Valid diastolic blood pressure (DBP) auscultatory measurements for lateral difference is \leq 10 mmHg.• Hemoglobin value \geq 11 g/dL.• CO value \leq 3.0% FCOHb.• Subject is comfortable to read and communicate in English*. 
* This is to ensure the subject can provide informed consent (as study materials are currently available in English only) and can comply with study procedures.

Exclusion criteria:	
Influenced by device warning labels:
 
• Subject is pregnant or breastfeeding.• Subject is experiencing dysrhythmia or arrhythmia. 
Influenced by study design/environment:
 
• Subject is concurrently participating in another research study.• Subjects not suitable for the investigation at the discretion of the clinical team including but not limited to the items below.
○ Subjects who do not pass the health assessment for safe participation in the study procedures.○ Inability to insert or difficulty with inserting an intravenous line in the subject's hand or arm and/or an arterial line in the radial artery of the subject's wrist.
Groups:	A targeted enrollment approach will be used to ensure ISO 81060-2-2018 ⁽¹⁾ requirements (specified under section 7.5.3) pertaining to sex, cuff size, and blood pressures distributions are met.

Study Title: Validation Study of Mean Arterial Pressure (MAP) Parameter of Masimo
INVSENSOR00073

Revision: 

Duration of the clinical investigation:	The expected duration of study enrollment is 1 to 3 months. Subject participation in the study will be approximately 180 minutes.
Study endpoint(s):	Accuracy and precision of mean arterial pressure (MAP) measured by Masimo INVSENSOR00073, in adult or adolescent patients, in comparison to radial arterial line.

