4. JUSTIFICATION FOR CLINICAL INVESTIGATION DESIGN PLAN

While arterial lines are the gold standard for blood pressure measurement, they are typically limited to high patient acuity situations due to their invasive nature and associated medical complications including hematoma, arterial thrombosis, and infection^(2, 3). Oscillometric non-invasive blood pressure measurement is the preferred choice in the majority of low and moderate patient acuity situations.

This is a clinical validation study of the mean arterial pressure parameter of Masimo INVSENSOR00073 against blood pressure measurements from invasive radial arterial line based on guidelines set forth in *ISO 81060-2, Non-invasive sphygmomanometers- Part 2: Clinical investigation of intermittent automated measurement type*.

Per *ISO 81060-2*, performance of Masimo INVSENSOR00073 needs to be investigated across a pre-specified distribution of blood pressures (detailed in section 8 below). Accordingly, in this study participants will undergo a blood pressure variation procedure using pharmaceuticals. Participants will be healthy volunteers, who will complete a clinical screening prior to being enrolled in the study to ensure subject eligibility as well as to reduce the occurrence of any potential harm that may arise because of study participation. Participants will be administered continuous infusions containing vasoactive medications and may participate in induced controlled hypertension (increased blood pressure) and/or induced controlled hypotension studies (decreased blood pressure). Consistent with other studies of blood

Study Title: Validation Study of Mean Arterial Pressure (MAP) Parameter of Masimo
INVSENSOR00073

Revision: 

pressure⁽⁴⁻⁸⁾, increasing and lowering of blood pressure will be achieved using [REDACTED] and [REDACTED] respectively⁽⁴⁻⁸⁾.

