7.5. Subjects

7.5.1. Inclusion Criteria

Influenced by study design:

- Subject is 18 to 40 years of age.
- Subject weighs a minimum of 110 lbs.
- Baseline heart rate ≥ 45 bpm and ≤ 90 bpm.
- Baseline blood pressure:

Systolic blood pressure ≤ 135 mmHg and ≥ 100 mmHg.

Diastolic blood pressure ≤ 95 mmHg and ≥ 55 mmHg.

If systolic blood pressure is lower than 100 mmHg and/or diastolic blood pressure is lower than 60 mmHg, subject passes an orthostatic blood pressure test.

Valid systolic blood pressure (SBP) auscultatory measurements for lateral difference is ≤ 15 mmHg.

Valid diastolic blood pressure (DBP) auscultatory measurements for lateral difference is ≤ 10 mmHg.

- Hemoglobin value ≥ 11 g/dL.
- CO value $\leq 3.0\%$ FCOHb.
- Subject is comfortable to read and communicate in English*.

* This is to ensure the subject can provide informed consent (as study materials are currently available in English only) and can comply with study procedures.

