7.5.2. Exclusion Criteria

Influenced by device warning labels:

- Subject is pregnant or breastfeeding.
- Subject is experiencing dysrhythmia or arrhythmia.

Influenced by study design/environment:

[figure not shown]
- Subject is concurrently participating in another research study.
- Subjects not suitable for the investigation at the discretion of the clinical team including but not limited to the items below.
 - Subjects who do not pass the health assessment for safe participation in the study procedures.
 - Inability to insert or difficulty with inserting an intravenous line in the subject's hand or arm and/or an arterial line in the radial artery of the subject's wrist.

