7.6.2.2. Health Assessment and Eligibility Determination

After informed consent, subjects will be screened to determine eligibility for study enrollment and safe participation in the study. Subjects must meet all inclusion criteria and none of the exclusion criteria to participate in the study. All subjects screened will be documented on the *Screening and Enrollment Log*. Subjects who do not meet the eligibility criteria will be considered screen failures and the reason for the status of screen failure will be documented on the *Screening and Enrollment Log*.

Information on subject demographics (including but not limited to sex, race and ethnicity, skin pigmentation, age, height, and weight), arms circumference, and a medical history may be collected.

- Pregnancy Screening:

Female subjects will be required to take a pregnancy test. Subjects will be notified of their pregnancy result and the result will be noted. Subjects will be excluded from the study if the result is positive.

- Vital Signs Screening:

Vital signs such as blood pressure, heart rate, and pulse oximetry measurements such as SpO₂, SpCO, and SpHb may be checked and recorded for subject safety monitoring.

Transient increases in blood pressure and heart rate can be expected during line placement, needle sticks, blood draw, etc. and may also be attributed to anxiety/nervousness relating to a new environment. For most participants, only the initial recorded blood pressure and/or heart rate determines a subject's qualification for the study. In the case where heart rate and blood pressure changes suggest participant discomfort or a potential safety concern, the participant will be removed from the study after qualifying, according to the discretion of medical and study staff.

Assessment of lateral difference in blood pressure measurements between the left and right arms will be done with simultaneous blood pressure reading in both arms. Simultaneous blood pressure reading in both arms will be performed using FDA-cleared auscultatory measure three times, following best practices (e.g., positioning the middle of the cuff on the patient's upper arm at the level of the right atrium [the midpoint of the sternum]). Study will only proceed if the lateral difference is ≤ 15 mmHg for the systolic blood pressure (SBP), and ≤ 10 mmHg for the diastolic blood pressure (DBP). Otherwise, the subject will be withdrawn from participating in the study.

- Venous and Arterial Access Screening:

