16. VULNERABLE POPULATION

16.1. Definition

Vulnerable population are research subjects, such as children, prisoners, pregnant women, handicapped, or mentally disable persons, or economically or educationally disadvantaged persons, who are likely to be vulnerable to coercion and undue influence. This study is not targeting these populations.

The federal regulations that govern the protection of human subjects require additional protection for the vulnerable population.

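### The synopsis endpoint extends MAP accuracy to adolescents, but the binding age limit of 18 to 40 years means none can be enrolled

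*Combined protocol and SAP*

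**What the plan says.** The only endpoint statement is in the synopsis (section 2, study endpoints). It gives accuracy and precision of MAP from the device "in adult or adolescent patients, in comparison to radial arterial line".

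The rest of the plan describes a narrower group:

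- **Age.** Section 7.5.1 states "Subject is 18 to 40 years of age", and the inclusion criteria in the synopsis say the same.
- **Force of the criterion.** Section 7.6.2.2 states "Subjects must meet all inclusion criteria and none of the exclusion criteria to participate in the study".
- **Health status.** Section 4 states "Participants will be healthy volunteers, who will complete a clinical screening prior to being enrolled in the study". Among the grounds for exclusion, section 7.5.2 lists "Subjects who do not pass the health assessment for safe participation in the study procedures".
- **Children.** Section 16.1 includes children in its list of vulnerable groups and then says "This study is not targeting these populations".
- **Targeted enrolment.** The synopsis limits this to the requirements "pertaining to sex, cuff size, and blood pressures distributions are met". Age is not among them.

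The objective (section 6), the accuracy calculation (section 8.2.1) and the acceptance criterion (section 8.2.2) do not say to which age group the result applies.

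**The concern.** An endpoint should describe people whom the trial can observe. This one names an age group that the plan's own entry criteria shut out, and it is the only endpoint wording in the document, so no second statement corrects it.

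What is at stake is the conclusion drawn from a pass. Section 18 commits the sponsor to posting results on a public registry. If the endpoint line is carried over as it stands, a mean error within 5 mmHg and a standard deviation of at most 8 mmHg would be reported for a population that includes adolescents. Someone who saw only the endpoint line could not tell that every observation came from healthy adults aged 18 to 40 years.

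**Working it through.** No power calculation or estimate is in dispute, so the check compares the population in the endpoint with the population that can be enrolled.

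**Step 1: the plan's own sample-size figures (section 8.1).** They reproduce, and none depends on age.

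- Minimum data points: 15 subjects × 10 measurements = 150, as stated.
- Sex quota: 0.30 × 15 = 4.5, rounded up to 5 males and 5 females, as stated.
- Cuff quota, with three sizes: 15 / (2 × 3) = 2.5, rounded up to 3 per size, as stated.
- With the planned 20 or so subjects, the ceiling is 20 × 10 = 200 data points.

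**Step 2: the two populations side by side.**

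| Feature | Endpoint (synopsis) | Enrolled population |
|---|---|---|
| Adults | named | yes, aged 18 to 40 years (synopsis; 7.5.1) |
| Adolescents | named | none: under 18 fails a binding criterion (7.5.1; 7.6.2.2) |
| Health status | called patients | healthy volunteers (4) |

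**Step 3: size of the mismatch.** The document does not define adolescent, and I read it as under 18. Ages below 18 and ages 18 to 40 do not overlap, so the number of adolescents who can be enrolled is 0 of about 20. At up to 10 measurements each, they contribute 0 of the 150 to 200 data points.

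**Step 4: is the extension justified elsewhere?** The visible text contains no second cohort, no bridging argument and no statement that adult results may stand for adolescents. Redaction does not explain the mismatch, since the endpoint sentence and the age criterion are both fully legible. The drug-induced pressure changes in section 7.6.3.3 widen the range of pressures tested, not the range of ages.

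**The case against.** The strongest reply has four parts.

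- **The wording is disjunctive.** Adults alone could satisfy a phrase joined by *or*, and the phrase may be a generic device category. Both readings are possible. The document states neither, and on the first the mention of adolescents does no work.
- **The endpoint is measured.** A reader might infer from the mismatch that the trial does not measure its endpoint at all. The documents do not support that. Section 8.2.1 defines the paired error against the radial arterial line, its mean and its standard deviation, and section 8.2.2 sets the limits. This part of the reply stands in full.
- **The upper age limit and the word patients are not contradictions of the same kind.** A reader might count adults over 40, and patients as opposed to volunteers, as further groups wrongly claimed. People aged 18 to 40 are adults, so the upper limit raises only the ordinary question of generalisability. Sections 3 and 7.6.2.2 use *patient* loosely for the person wearing the cuff, the latter while describing the screening of these same volunteers. This part also stands.
- **The harm is conditional.** The plan makes no labelling claim for adolescents, and section 18 does not say that this line will be the results statement. The age range appears in the same synopsis, so a reader of the whole plan is unlikely to be misled. That is true. It limits the weight of the point but does not make the endpoint line correct.

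**Conclusion.** The point holds as a mismatch between the endpoint's stated population and the enrolled one. The adolescent part of the endpoint can have no data behind it (0 of about 20 subjects), and nothing in the plan justifies the extension. The result can support a statement about healthy adults aged 18 to 40 years.

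It would be wrong to go further and call the endpoint unmeasured or the design invalid. The defect is confined to one line and affects what may be concluded, not how the error is computed or judged.

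The conclusion rests on two assumptions: that adolescent means under 18, and that no rationale sits in text that was withheld or in a separate document. If adolescence were taken to run past 18, the youngest enrollees might qualify, but no quota would ensure that any were enrolled. The line should be corrected before results are posted.

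**What to change.** In the synopsis endpoint, delete *or adolescent* and describe the population as the one enrolled. For example: accuracy and precision of MAP measured by the device in healthy adult volunteers aged 18 to 40 years, compared with the radial arterial line. Use the same population in the posted results.

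If the sponsor wants to keep the wider wording, the plan should say what category the phrase refers to and give an explicit rationale for applying adult results to adolescents.

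The rewording costs one synopsis line, processed as an amendment under section 10, and it narrows the claim. No procedure, sample size, error formula or acceptance limit changes.

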3. DESCRIPTION OF THE INVESTIGATIONAL DEVICE

 is a continuous, scalable, patient-worn, vital signs monitor , which provides the versatility of a bedside monitor in a wearable device.

 monitors a wide range of physiological parameters. Designed to scale up or down with patient acuity,  combines the reliability and accuracy of a bedside monitor with the comfort and freedom of a wearable device, allowing for ambulation and movement during continuous monitoring. Suitable for use across the continuum of care,  offers advanced flexibility and is easily scalable to accommodate surges in patient volume and each patient's level of acuity.

The focus of this study is on the validation of the mean arterial pressure (MAP) parameter of Masimo INVSENSOR00073. Masimo INVSENSOR00073 provides systolic, diastolic, and mean arterial blood pressure readings through an oscillometric method. An oscillometric method of blood pressure measurement is a noninvasive method that monitors the amplitude of cuff pressure changes during cuff deflation to determine arterial blood pressure. Masimo INVSENSOR00073 consists of a reusable module and a disposable cuff, which plug into the  device, or a laptop for data collection purposes.

For blood pressure measurements, the cuff is wrapped around the non-dominant arm, making sure that the cuff's Artery Marker is aligned over the brachial artery. To locate the brachial artery, one should place the pads of his/her index and middle fingers halfway between the shoulder and elbow, in the middle of the inner arm, between the biceps and triceps muscles. The cuff should fit comfortably around the patient's arm for maximum oscillometric signal quality. The lower edge of the cuff should be located 2 cm above the antecubital fossa (interior bend of the elbow).

4. JUSTIFICATION FOR CLINICAL INVESTIGATION DESIGN PLAN

While arterial lines are the gold standard for blood pressure measurement, they are typically limited to high patient acuity situations due to their invasive nature and associated medical complications including hematoma, arterial thrombosis, and infection^(2, 3). Oscillometric non-invasive blood pressure measurement is the preferred choice in the majority of low and moderate patient acuity situations.

This is a clinical validation study of the mean arterial pressure parameter of Masimo INVSENSOR00073 against blood pressure measurements from invasive radial arterial line based on guidelines set forth in *ISO 81060-2, Non-invasive sphygmomanometers- Part 2: Clinical investigation of intermittent automated measurement type*.

Per *ISO 81060-2*, performance of Masimo INVSENSOR00073 needs to be investigated across a pre-specified distribution of blood pressures (detailed in section 8 below). Accordingly, in this study participants will undergo a blood pressure variation procedure using pharmaceuticals. Participants will be healthy volunteers, who will complete a clinical screening prior to being enrolled in the study to ensure subject eligibility as well as to reduce the occurrence of any potential harm that may arise because of study participation. Participants will be administered continuous infusions containing vasoactive medications and may participate in induced controlled hypertension (increased blood pressure) and/or induced controlled hypotension studies (decreased blood pressure). Consistent with other studies of blood

Study Title: Validation Study of Mean Arterial Pressure (MAP) Parameter of Masimo
INVSENSOR00073

Revision: 

pressure⁽⁴⁻⁸⁾, increasing and lowering of blood pressure will be achieved using [REDACTED] and [REDACTED] respectively⁽⁴⁻⁸⁾.

While a blood pressure variation procedure is not free of risks, risks have been mitigated. Potential hazards associated with use of [REDACTED] and [REDACTED] include overdose and overreaction to the drug. There is also a possibility of cyanide poisoning, though highly unlikely. Accordingly, subjects will start at [REDACTED] $\frac{\mu\text{g}/\text{kg}}{\text{min}}$ of [REDACTED] and [REDACTED]. An increase of dose will only occur if the subject is asymptomatic. Safety drugs as outlined in Table 2 (see section 7) will also be used should it be deemed necessary by the presiding clinician. The infusion will be stopped through safety clamp or stopcock immediately, should continuation with the procedure be deemed unsafe for the participant.

Similarly, an invasive A-line placement for blood pressure measurements is not free of risks; accordingly, to mitigate risks, participants are monitored by study staff (including an Advanced Cardiovascular Life Support (ACLS)-certified physician) for the duration of blood pressure variation procedure, provided with post care instructions discharge, and can reach Masimo in the case of any complications after discharge.

Once the blood pressure variation procedure has been completed, the subject will be monitored until their pressure is within 10 mmHg of their baseline and they have been asymptomatic for approximately 30 minutes.

Other requirements of *ISO 81060-2* pertain to sex and cuff size distributions (detailed in section 8 below). Accordingly, a targeted enrollment approach will be used to select participants across the spectrum needed for the validation study.

5. BENEFITS AND RISKS OF THE INVESTIGATIONAL DEVICE, CLINICAL PROCEDURE, AND CLINICAL INVESTIGATION

5.1. Anticipated Clinical Benefits

There will be no direct benefit to the enrolled subjects. Benefit would be to the society at large, through paving the path for development and availability of a tetherless blood pressure monitor, which would provide reliable and accurate monitoring with the comfort and freedom of a wearable device.

5.2. Anticipated Adverse Events

The following adverse events are anticipated:

5.2.1. Risks Associated with the Study Devices

The noninvasive devices used in this study are similar in technology and design to commercially available FDA-cleared devices and hence pose minimal risk to subjects. A *Clinical Investigation Risk Assessment* has been conducted and documented where relevant biological, chemical, electrical, and mechanical hazards associated with Masimo INVSENSOR00073 were identified and mitigated as used in this clinical investigation. Refer to the *Investigator Brochure (IB)* and/or *Operator's Manual* for full description of warnings and cautions and instructions.

There is a risk of temporary discomfort to subjects at the blood pressure cuff placement location, including temporary skin irritation, redness, and itching. In the absence of intact skin (e.g., cuts or abrasions) at or near the application site, the subject will be disqualified from the study to avoid potential discomfort.

Device warning labels are as follows:

- Frequently check the blood pressure monitoring site to ensure adequate circulation to prevent patient injury.

- Do not apply the cuff to a limb that is on the same side of a mastectomy.
- Do not use or stop blood pressure measurements if the patient appears to be affected by the pressurization of the cuff due to a physical condition (e.g., pregnant, pre-eclamptic).
- Avoid too frequent blood pressure measurements to prevent injury to the patient due to blood flow interference.
- Do not attach the cuff to a limb being used for IV infusions or any other intravascular access, therapy or an arterio-venous (A-V) shunt. The cuff inflation can temporarily block blood flow, potentially causing harm to the patient.
- Before applying the cuff on the patient, confirm the cuff size is appropriate.
- When a blood pressure measurement error code occurs, any blood pressure values reported should be disregarded.
- Do not apply the blood pressure cuff over a wound to avoid further injury.
- A compressed or kinked connection hose may cause continuous cuff pressure resulting in blood flow interference and potentially harmful injury to the patient.

